7.2. General Methodology

Descriptive statistics will be used to summarize patient characteristics. For categorical variables, the description will consist at least of the sample size, numbers of missing data and valid data, the frequency and the percentage of each category. Denominators for calculation of percentages will be taken as the number of subjects with available (not missing or unknown) observations in the specified patients sets and groups unless otherwise stated. Percentages will be presented with no decimal (or one decimal, if appropriate) and rounded to the nearest integer. For continuous variables, the description will consist at least of the sample size (N), number of subjects with non-missing observation (n), mean, standard deviation, standard error, minimum, median and maximum. For $n < 3$, only mean, minimum and maximum will be displayed. In general, minimums and maximums will be presented to the same level of accuracy as the raw data; means and medians will be presented to 1 further decimal place; if appropriate, standard deviation and standard error will be presented to 2 further decimal places.

Device data metrics will be derived in a real-world data setting using all the device data collected during the patient study exposure.

It is anticipated that SAS 9.4 or later (SAS Institute Inc., Cary, NC, USA) will be used to perform all statistical analyses. Statistical tests will be based on a one-sided significance level of 0.05, and possible interaction effects will be evaluated at a significance level of 0.10. No adjustments for multiple comparisons will be performed. Additional exploratory analyses will be conducted as deemed appropriate and described as ad-hoc analysis in the study report.

7.3. Center Pooling

The study is a multicenter trial and a multicenter impact on primary outcomes will be investigated. A description by means of summary statistics on primary outcomes by sites will be provided.

7.4. Handling of Missing, Unused, and Spurious Data and Dropouts

Since the impact of missing data is expected to be small, no imputation of missing data will be performed.

In the case of dates collected at baseline with missing day and/or month the next procedure will be applied. A missing day and month will be imputed using the month 'July 1' and a missing day will be imputed with the day '15'. This applies only to dates related to medical history and baseline information with missing month and/or day.

For per protocol analysis, if HbA1c is collected out of window (-30 days from the date of actual Baseline visit and \pm 30 days from the date of actual Follow-up visit), HbA1c will be considered missing for that period/visit.

Outliers and influential observations will be identified via graphical plots. Once outliers or influential observations are identified, the study team will be informed and according to their decision the analysis for primary endpoint may be repeated using a statistical method robust against outliers. Additional exploratory analyses will be conducted as deemed appropriate.

7.5. Adjustments for Multiple Comparisons

No adjustments for multiple comparisons will be performed.

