4.2. Purpose

Medtronic France SAS is sponsoring the CIP328 EQOL study, a Post-Market non-interventional, prospective, local, single-arm, multi-center non-randomized clinical study. The purpose of this study is to evaluate the impact on glycemic control and quality of life of patients using the MiniMed™ 780G System for the treatment of Type 1 diabetes, in real life settings in France to support reimbursement of the MiniMed™ 780G in France. This data will complete the available data from international pivotal studies, as it is highly recommended by the French authorities to provide local data on glycemic control, quality of life and treatment satisfaction in real life conditions.

5. Objectives and Endpoints

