The Hypoglycemia Fear Survey (HFS) originally was developed to measure behaviors and worries related to fear of hypoglycemia (FOH) in adults with type 1 diabetes. Both the original HFS (HFS-I) and the revised version (HFS-II) are composed of two subscales, the Behavior (HFS-B) and Worry (HFS-W). HFS-B items describe behaviors in which patients may engage to avoid hypoglycemic episodes and/or their negative consequences (e.g., keeping blood glucose [BG] levels above 150 mg/dL, making sure other people are around, and limiting exercise or physical activity). HFS-W items describe specific concerns that patients may have about their hypoglycemic episodes (e.g., being alone, episodes occurring during sleep, or having an accident). Alternative versions of the HFS have been developed for use with pediatric patients with type 1 diabetes and their parents and will be used in the study (14–16).

Following the objective to assess the new patient's pathway and the benefits of MiniMed™ 780G system in real-life settings, the study design aims to follow routine practice, with before/after comparison of the data to show the benefit of the MiniMed™ 780G system on glycemic parameter, patient treatment satisfaction and quality of life.

Due to the nature of the study, no data monitoring committee is needed.

7. Product Description

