The primary analysis will be performed on the Intention To Treat (ITT) set and a sensitivity analysis will be performed using the Per Protocol set including all subjects that were compliant with the protocol.

The ITT includes all patients enrolled in the study those sign Data Release Form, fulfill the inclusion and exclusion criteria. The ITT will be used for all endpoints and safety evaluation. For patients who dropout the analyses will include all data up to the point of their last data collection.

The PP includes all patients enrolled in the study those sign Data Release Form, fulfill the inclusion and exclusion criteria and having at least 70% of time using the Auto Mode. The PP set will be used for all endpoints.

The primary endpoint on efficacy defined as the change of TIR at 6 months from Auto Mode activation at baseline will be analyzed by means of paired (samples) t-test or Wilcoxon signed rank sum test according to the normal or non-normal distribution. The mean change will be displayed together with their 95% confidence interval (95%CI). Additional exploratory analysis on the TIR change over time (baseline, 3, 6 and 12 months follow-up) will be analyzed by means of mixed models for repeated measures. The dependent variable will be pre-log transformed depending on normal or non-normal distribution. The model will have the clinical outcomes as dependent variables and baseline values and visits as explanatory variables. All assumptions for regression models will be performed by assessment of plots of the residual values. Difference between visits means will be tested by applying contrast on the estimated model. The plot for the mean change over time will be

reported.

The secondary endpoint on satisfaction defined by the DTSQc will be analyzed by means of one sample Z- score test. The DTSQc has six items related to treatment satisfaction and two other items assess perceived frequency of hyperglycemia and hypoglycemia. Each item has a maximum of 3 (more satisfied now) and a minimum of -3 (less satisfied now) with a midpoint of 0 reflecting no change. The scale total is computed by adding 6 items (1,4,5,6,7,8) and the 2 items on hypo/hyperglycemia will be analyzed separately. Previous studies on patients treated with MiniMed™ 640G pump have shown a good satisfaction using the DTSQc questionnaire. The sample size estimated would also allow us to demonstrate a positive DTSQc satisfaction score.

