7.1.3. Analysis Sets

The following subject sets will be used for the analysis:

- The Intention To Treat (ITT) includes all patients enrolled in the study with signed Data Release Form, fulfill the inclusion and exclusion criteria. The ITT will be used for all endpoints and safety evaluation.
- The Per Protocol (PP) includes all patients enrolled in the study with signed Data Release Form, fulfill the inclusion and exclusion criteria and having at least 70% of time using the Auto Mode during the 6-month follow up. The PP set will be used for all endpoints.

The primary analysis will be performed on the ITT set. As sensitivity analysis the PP set will be used. The following table shows how each population set will be used for analyses:

Population set	Baseline assessment	Primary Endpoint	Secondary Endpoints	Adverse Events
PP	✓	✓*	✓	
ITT	✓	✓	✓	✓

* The primary endpoint on the PP population will be considered as sensitivity analysis

For patients who dropout, the analyses will include all data up to the point of their last data collection.

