7.9. Evaluation of Objectives

In this section a detailed information about each objective is included together with calculations and derivations of outcome parameters, analysis methods, datasets analyzed (PP and ITT). For each endpoint will be reported at least summary statistics table. All the objectives will consider two study phases calculated as defined in section 7.7. The secondary endpoints on questionnaires will include three subpopulations according to the age at the Consent date: Adult (≥ 18 years old), Teen (13-17 years old) and Parent (7-12 years old). This subpopulation definition will be maintained over the study visits.

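### Secondary endpoints are each tested at one-sided 0.05 with no error control, no order and no gate on the primary, and the two documents disagree on which of them are exploratory

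*SAP*

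**What the plan says.** **Level and adjustment.** SAP 7.2 sets one rule for all tests: "Statistical tests will be based on a one-sided significance level of 0.05". SAP 7.5 consists of one statement: "No adjustments for multiple comparisons will be performed". Protocol 12.3 says the same on both points.

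**Primary.** There is one primary endpoint at one time point, the change in TIR from run-in to 6 months, analysed on the ITT set (SAP 7.1.3, 7.9.1).

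**Secondary.** Six objectives follow, with no order.
- SAP 7.9.5 to 7.9.8 plan paired tests for DQoL, HFS, HbA1c and DTSQs, with assessments at both 6 and 12 months.
- DTSQc is tested at 6 months only (SAP 7.9.4).
- TIR and four other sensor-glucose metrics are modelled every three months (SAP 7.9.3, 7.9.7).
- SAP 7.9 adds: "The secondary endpoints on questionnaires will include three subpopulations according to the age at the Consent date".

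**Status.** Protocol 12.3 introduces one analysis as "Additional exploratory analysis on the TIR change over time", while Protocol 5.2 and SAP 4.2.1 list it as the first secondary objective. Of DTSQc, Protocol 12.3 says: "The sample size estimated would also allow us to demonstrate a positive DTSQc satisfaction score". SAP 7.9.4 says that this endpoint was not powered for testing, and then tests it.

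**Use.** The study is meant "to support reimbursement of the MiniMed™ 780G in France" (Protocol 4.2). The before/after design is intended "to show the benefit of the MiniMed™ 780G system on glycemic parameter, patient treatment satisfaction and quality of life" (Protocol 6.1).

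**The concern.** A plan may leave secondary tests unadjusted if it says that they are descriptive. This plan does not. In SAP 7.2 the word exploratory applies only to additional analyses reported as ad hoc, so it does not cover the tests in SAP 7.9.3 to 7.9.8. The Protocol gives one of these analyses two statuses, and attaches confirmatory language to another that the SAP says is unpowered.

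The results are to support a reimbursement case on glycaemia, satisfaction and quality of life. As written, nothing prevents a single secondary p-value below 0.05, at either visit or in one age group, from being presented as shown benefit, even if the primary TIR test fails. The stated 5% does not describe the chance of a false finding somewhere among the secondary results.

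**Working it through.** **The plan's own figure.** The sample size serves the primary test only. With the Protocol's SD of 16 and correlation 0.5, the SD of the paired difference is 16 × √(2 × (1 − 0.5)) = 16. For a 3-point gain, one-sided 0.05 and 90% power, n = (16 × (1.645 + 1.282) / 3)² = 243.6. That is 244 by the normal approximation and 245 by the exact t calculation, so the stated 245 pairs reproduces; 245 / 0.8 = 306.25, stated as 306. (The SAP prints SD 14 with the same 245. SD 14 would need 188, which is a separate discrepancy.) Neither document gives a calculation for DTSQc or any other secondary endpoint.

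**Counting the tests.** The SAP gives no count. Two defensible ones are:
- One test per endpoint: TIR, four other sensor-glucose metrics, HbA1c, DTSQc, DTSQs, DQoL, HFS = 10.
- The tests that follow from SAP 7.9.4 to 7.9.8 if each age group is tested separately: DTSQc 3 groups × 1 time = 3; DQoL 2 × 2 = 4; HFS 3 × 2 = 6; HbA1c 2; DTSQs 3 × 2 = 6. Total 3 + 4 + 6 + 2 + 6 = 21.

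Separate age-group tests are an inference. It is a natural one because the raw totals are on different scales: DTSQc runs to ±18, ±30 and ±36; DTSQs to 36, 60 and 72; HFS has 33, 25 and 26 items.

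**Chance of at least one false positive if every tested secondary effect is null.** For k independent tests this is 1 − 0.95^k. For a common correlation r it is 1 − E[Φ((1.645 − √r·X) / √(1 − r))^k], with X standard normal. The documents give no correlations among these tests, so a range is assumed.

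| Tests | r = 0 | r = 0.5 | r = 0.8 |
|---|---|---|---|
| 10 | 40% | 25% | 15% |
| 21 | 66% | 35% | 19% |

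The expected number of false positives does not depend on correlation: 10 × 0.05 = 0.5, or 21 × 0.05 = 1.05.

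**What control would cost.** A fixed sequence after the primary tests each step at the full one-sided 0.05, holds the familywise error at 0.05 and needs no more patients. Splitting alpha over the six secondary objectives (0.05 / 6 = 0.0083) would cut power from 90% to 70% at 245 pairs and a standardised effect equal to the primary's (3/16).

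**The case against.** The strongest defence is that this is a single-arm, non-interventional post-market study with one clear primary endpoint. The absence of adjustment is disclosed in both documents, mean changes come with 95% confidence intervals, and the SAP goes to the French health authority before the analyses (Protocol 14.7.4). No passage says that a secondary p-value below 0.05 counts as shown benefit. This stands in part: it is why labelling the tests descriptive is enough. It does not remove the conflicting labels or the sentence on demonstrating DTSQc.

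The error rates also require every tested secondary effect to be null, although Protocol 12.1 reports TIR gains of 5 to 7 points with the predecessor system. That stands, and the figures are conditional. They do not depend wholly on a device with no effect: if all glycaemic effects were real and only the 3 + 4 + 6 + 6 = 19 questionnaire totals were null, the chance would be 62%, 47% or 34% at within-group correlations of 0, 0.5 and 0.8, with age groups independent.

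Four stronger readings are tempting and are not supported:
- **About 41 tests.** This adds 20 visit contrasts for five sensor-glucose metrics at four visits. SAP 7.9.3 and 7.9.7 specify models and name no visit contrast. Protocol 12.3 mentions contrasts for TIR and HbA1c only.
- **A false claim is likely, at 88%.** That needs 41 independent tests with every null true. The metrics share patients and a run-in baseline, and some are nested in others. At common correlations of 0.5 and 0.8 even 41 tests give 44% and 23%.
- **No deciding time point anywhere.** The primary and DTSQc each have one, at 6 months.
- **The per-protocol set is a second route to a claim.** The SAP 7.1.3 footnote, "The primary endpoint on the PP population will be considered as sensitivity analysis", covers only the primary, but the text above its table calls that set a sensitivity analysis in general terms.

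**Conclusion.** The point holds for the secondary endpoints only. They are formally tested at one-sided 0.05 with adjustment ruled out, no order and no dependence on the primary. DQoL, HFS, DTSQs and HbA1c have two time points with neither named as decisive. The documents contradict each other on the status of TIR over time and of DTSQc.

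If the tested secondary effects were all null, the chance of at least one false-positive secondary result would be about 15% to 40% with 10 tests and about 19% to 66% with 21, against a nominal 5% per test. Both ranges rest on assumed common correlations from 0.8 to 0, and the counts are this review's, not the SAP's. Even the most favourable case is three times the nominal level. The defect is worth correcting because it governs what the study may claim, but it does not threaten the primary analysis.

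**What to change.** In SAP 7.5 and Protocol 12.3, replace the blanket statement with one of two rules.

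1. The primary TIR test on the ITT set, at one-sided 0.05, is the only confirmatory test. Secondary results are reported as estimates with confidence intervals, their p-values are descriptive, and none is described as demonstrated.
2. If confirmatory secondary claims are wanted for the reimbursement file, name a short list with one time point and one prespecified test each (for example HbA1c at 6 months, then one test each for DTSQc, DQoL and HFS). Test it on ITT in fixed sequence at one-sided 0.05, only after the primary succeeds, and stop at the first non-significant result. Everything else is exploratory.

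Under either rule, delete the Protocol 12.3 sentence about demonstrating a positive DTSQc score, and give TIR over time the same status in both documents.

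The cost is wording in two documents, with no new data and no more patients. The downside is that fewer secondary results can be claimed as demonstrated.

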7.6. Demographic and Other Baseline Characteristics

Demographic and Baseline variables will be collected through:

- Demographics: age, sex
- Medical history: HbA1c (collected up to 30 days before enrollment), last treatment, Name of the last pump device, Date of the first pump treatment, Years since diagnose of T1D, Number of severe hypoglycemia in the last year
- Questionnaires: DTSQs, DQoL (except for patients between 7 and 12 years old), HFS

At the end of the run-in period, the following data will be also collected:

- Mean TIR (70-180mg/dL)
- Mean Time spent of sensor glucose value below 70mg/dL and below 54mg/dL
- Mean Time spent of sensor glucose value above 180mg/dL and above 250mg/dL
- Number of bio-chemical hypoglycemic event per week

7.7. Treatment Characteristics

Duration of Study Exposure will be measured in days starting from the point of enrollment (informed consent signed and inclusion/exclusion criteria confirmed) through and including the time of study exit. The study has two phases:

The Run-In phase starts at the Enrolment (Consent date) and it ends at the Auto Mode activation date. It is expected that the Run-In phase will last 2 weeks.

The Study phase starts at the Auto Mode activation (end of Run-In phase) and it ends at 12 month follow up. The study phases exposures are calculated as:

- Duration of study exposure (days) = (Study Exit date – date of Enrollment(Consent) +1).
- Duration of Run-In phase exposure (days) = (date of Automode Activation – date of Enrollment(Consent) +1).
- Duration of Study phase exposure (days) = (date of Study exit – date of Automode Activation +1).

Extent of study exposures will be presented in a summary table.

7.8. Interim Analyses

No interim analysis is planned for this study.

7.9. Evaluation of Objectives

In this section a detailed information about each objective is included together with calculations and derivations of outcome parameters, analysis methods, datasets analyzed (PP and ITT). For each endpoint will be reported at least summary statistics table. All the objectives will consider two study phases calculated as defined in section 7.7. The secondary endpoints on questionnaires will include three subpopulations according to the age at the Consent date: Adult (≥ 18 years old), Teen (13-17 years old) and Parent (7-12 years old). This subpopulation definition will be maintained over the study visits.

7.9.1. Primary Endpoint

The primary endpoint on efficacy defined as the change of TIR at 6 months, calculated starting from the Auto Mode activation (Study phase) to the 6-months, with baseline (Run-In phase) will be analyzed by means of paired (samples) t-test or Wilcoxon signed rank sum test according to the normal or non-normal distribution.

The TIR will be calculated as the proportion (%) of sensor glucose concentration measurements within the target range of 70-180 mg/dL (3.9-10.0 mmol/L) on the total sensor glucose measurements.

The mean change will be displayed together with their 95% confidence interval (95%CI).

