12.2. Sample size Calculations

The sample size was determined using a one sample paired test assuming a one-sided type I error rate of 0.05 and a power greater than 90%. The TIR at baseline is assumed to be 60% and the TIR at 6 months follow up (TIR calculated using overall 6 months CGM data) is assumed to be 63% with same standard deviation as 16% and a correlation as 0.5. Thus, the hypothesis to be tested is:

$$H_0: \mu\text{TIR6m} - \mu\text{TIR baseline} = d_0$$

$$H_A: \mu\text{TIR6m} - \mu\text{TIR baseline} > d_0$$

where $d_0 = 3$ is the expected increase of TIR at 6 months. The sample size needed to demonstrate this hypothesis is 245 paired assessments per subject. The calculation is adjusted for loss-to-follow-up and protocol failures, including potential subjects with less than 70% of the time in Auto Mode with an assumption considering an attrition rate of 20%. The total number of subjects to be enrolled is 306.

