An overview of data collection is given in the Table 1.

Table 1: Schedule of assessments

Data collection	Enrollment /Baseline	6-month Follow-up (±45 days)	12-month Follow-up (±45 days)
Data Release Form	✓		
Inclusion and exclusion criteria	✓		
Demographics	✓		
Medical history	✓		
HbA1c¹	✓	✓	✓
Auto Mode Activation Date	✓		
Ensure that CareLink™ Personal upload was done²	✓ ⁴	✓	✓
CGM data	✓	✓	✓
Study Exit			✓
Study Deviation	Upon occurrence		
QUESTIONNAIRES :			
DTSQs	✓	✓	✓
DTSQc		✓	
DQoL³	✓	✓	✓
HFS	✓	✓	✓

1. Available HbA1c value collected up to 30 days before enrollment and more or less 30 days from 6-month and 12-month follow up visits can be used.
2. CareLink™ data should be uploaded via Bluetooth connectivity from the devices or via USB connection as per clinical practice, i.e. once a week. CareLink™ Data evaluation will be done every 3 months for secondary objectives.
3. DQoL will not be administered in case patient is between 7 and 12 years old.
4. Baseline CGM data will be collected before Auto Mode activation at the end of the run-in phase

6. Determination of Sample Size

The sample size was determined using a one sample paired test assuming a one-sided type I error rate of 0.05 and a power of 90%. The TIR at baseline is assumed to be 60% and the TIR at 6 months follow up (TIR calculated using overall 6 months CGM data) is assumed to be 63% with same standard deviation as 14% and a correlation as 0.5. Thus, the hypothesis to be tested is:

$$H_0: \mu_{TIR6m} - \mu_{TIR \text{ baseline}} = d_0$$

$$H_A: \mu_{TIR6m} - \mu_{TIR \text{ baseline}} > d_0$$

where $d_0 = 3$ is the expected increase of TIR at 6 months. The sample size needed to demonstrate this hypothesis is 245 paired assessments per subject. The calculation is adjusted for loss-to-follow-up and protocol failures, including potential subjects with less than 70% of the time in Auto Mode and with an assumption considering an attrition rate of 20%. The total number of subjects to be enrolled is 306.

[figure not shown]
7. Statistical Methods

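### The primary TIR test is left to the observed distribution with no criterion; if the changes are skewed, a switch to Wilcoxon no longer tests the mean on which the plan rests

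*SAP*

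**What the plan says.** SAP 7.9.1 states that the primary endpoint "will be analyzed by means of paired (samples) t-test or Wilcoxon signed rank sum test according to the normal or non-normal distribution". Protocol 12.3 has the same either/or: "paired (samples) t-test or Wilcoxon signed rank sum test according to the normal or non-normal distribution". Protocol 12.3 leaves the detail of the methods to the SAP, but the SAP adds none. Neither document gives a normality test, a threshold, a graphical rule or a default, or says which variable is examined.

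The rest of the primary analysis is about the mean:

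- **Hypothesis.** Protocol 12.2 and SAP section 6 write it as a difference between mean TIR at 6 months and mean TIR at baseline.
- **Sample size.** Both documents call for 245 pairs. The Protocol plans "with same standard deviation as 16% and a correlation as 0.5"; the SAP has "with same standard deviation as 14% and a correlation as 0.5".
- **Estimate.** Protocol 12.3 and SAP 7.9.1 show the mean change with a 95% confidence interval, whichever test is used.

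On the level, SAP 7.2 says: "Statistical tests will be based on a one-sided significance level of 0.05".

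**The concern.** With about 245 pairs, the paired t-test is close to valid for the mean without normal data, so the switch protects against little. When the changes are skewed, the switch alters the question. The signed-rank test is then centred on the pseudomedian, which differs from the mean. The primary p-value would address one quantity while the hypothesis, the power calculation and the displayed interval address another.

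Two things are at stake. Under skew, the test can reject too often or too rarely for the mean, and it can contradict the interval beside it. Whatever the shape, an unblinded single-arm study would have a primary test that is not settled before the data are seen.

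**Working it through.** **1. The plan's own figure.** Inputs from Protocol 12.2: SD 16 at each time, correlation 0.5, difference 3, one-sided 0.05, 90% power.

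- SD of change = sqrt(2 × 16² × (1 - 0.5)) = 16.
- Paired t-test by noncentral t: n = 245, power 90.0%. This matches the stated 245.
- Attrition: 245 / 0.8 = 306.25, against 306 stated.
- With the SAP's SD of 14, the SD of change is 14. The same calculation gives n = 188, or 95.5% power at 245.

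So 245 is a paired t-test sample size for a mean change, tested against zero. Both documents write the null as equal to d0 = 3, but the figure reproduces only with a null of zero, which I use below.

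**2. What Wilcoxon targets under skew.** For gamma-shaped changes with mean 0 and SD 16, the pseudomedian is -0.67 at skewness +0.5 and -1.31 at +1; it is +0.67 at -0.5 and +1.29 at -1. The standard error of the mean is 16 / sqrt(245) = 1.02, so these shifts are about 0.7 to 1.3 standard errors.

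**3. Simulation of the two-stage rule.** Assumptions not in the documents: Wilcoxon (normal approximation) if Shapiro-Wilk p < 0.05, otherwise paired t; null of zero; the shapes listed. n = 245, SD of change 16, one-sided 0.05, 4,000 trials per case (Monte Carlo SE at most 0.8 points). A dash means not tabulated.

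| Shape of changes | Switched to Wilcoxon | Rejects at mean change 0 | Power at +3 | At +3: not significant, but 95% CI excludes 0 |
|---|---|---|---|---|
| Normal | about 5% | 4.8% | - | 0.1% |
| Symmetric, t with 5 df | 87-89% | 5.4% | 93.9% | - |
| Skewness -0.25 | 27-29% | 7.2% | - | - |
| Skewness -0.5 | 80-82% | 14.3% | 95.6% | - |
| Skewness -1 | 100% | 37.4% | 99.1% | - |
| Skewness +0.25 | 27-29% | 4.0% | 86.1% | - |
| Skewness +0.5 | 80-82% | 1.5% | 74.3% | 9.6% |
| Skewness +1 | 100% | 0.2% | 50.5% | 34.9% |

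The fixed paired t-test rejects 4.5-6.2% at mean change 0 and has 89-92% power at +3.

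**4. Sensitivity to SD and effect.**

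- SD 14, gain 3: power is 86.0% (+0.5) and 68.6% (+1), against 96-97% for the t-test. Contradictions occur in 7.1% and 25.0% of trials.
- SD 16, gain 5: power is 99.8% (+0.5) and 97.9% (+1).

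**5. Cross-check.** With 20,000 trials, always using Wilcoxon rejects 15.7% and 35.9% at mean change 0 (skewness -0.5 and -1), and has 74% and 51% power at +3 (skewness +0.5 and +1). These are close to the two-stage rates, as expected when most trials switch.

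**6. Interval level, a separate and smaller point.** With 244 df, the one-sided 0.05 test needs a mean above 1.651 × 16 / sqrt(245) = 1.69. A two-sided 95% interval excludes 0 only above 1.970 × 16 / sqrt(245) = 2.01. Between these limits the test is significant but the interval includes 0. At a true gain of 3 the probability is 0.900 - 0.832 = 6.8%. With SD 14 the limits are 1.48 and 1.76, and the probability is 0.955 - 0.916 = 3.9%.

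**The case against.** **The size rests on assumptions.** Skewness, gamma shape, the Shapiro-Wilk rule and the null of zero are not in the documents. Under normal or symmetric heavy-tailed changes the rule keeps its level. This stands: the table shows a range and does not forecast this trial.

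**At the effects the Protocol cites, the choice hardly matters.** Section 12.1 reports gains of 5.0 points (SDs 11.9 and 8.4) and 6.8 points (SDs 10.9 and 8.2) in an earlier study. With a correlation of 0.5, the SDs of change are sqrt(11.9² + 8.4² - 11.9 × 8.4) = 10.6 and sqrt(10.9² + 8.2² - 10.9 × 8.2) = 9.8. In simulation at those values both procedures rejected in every trial for skewness from -1 to +1. At a gain of 3 with SD 10.6 and skewness +1, the rule still had 95% power and 4% contradictions. This also stands, but those data come from an earlier system over 3 months, and the Protocol deliberately plans for 3 points and SD 16.

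**The two harms exclude each other.** Inflated error needs left skew; lost power needs right skew. Only one can occur, and the documents do not say which.

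**The plan gives partial cover.** Both tests are named in advance, and the mean with its interval is always shown. SAP 7.4 also allows a repeat analysis by a robust method. That repeat is optional, is decided by the study team after plots, and does not say how the primary test is chosen. The gap narrows but stays open.

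**The interval level is only a reporting matter.** Agreed; it does not inflate error.

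**Conclusion.** The concern holds. The missing criterion is plain in both documents and does not depend on any assumption. The statistical consequence depends on skew, which the documents do not describe. At the planning effect of 3 points and SD 16, moderate skew (0.5 in absolute value) either raises the one-sided error to about 14% or lowers power to about 74%, according to its direction. Skewness of 1 gives about 37% or 51%. For symmetric changes there is no error problem, and for gains of 5 points or more the result would seldom change. The rule should be corrected before analysis, but it does not undermine the design: the planned sample size already fits the simpler test.

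**What to change.** Replace the either/or rule in SAP 7.9.1, and in Protocol 12.3 to match, with text such as:

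> The primary analysis is the paired t-test on the mean change in TIR in the ITT set, at one-sided 0.05, whatever the observed distribution. The mean change is shown with its one-sided 95% lower bound (the lower limit of the two-sided 90% interval), which matches the test, and with the two-sided 95% interval. The Wilcoxon signed-rank test with a Hodges-Lehmann estimate and interval is a labelled sensitivity analysis.

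The text should also state the null value. The 245 pairs imply zero, so the hypothesis in Protocol 12.2 and SAP section 6 needs to be reconciled with it.

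**Cost.** The sample size stays at 245 pairs and 306 enrolled. Under symmetric heavy tails (t with 5 df) at a gain of 3, the fixed t-test has 90.2% power against 93.9% for the two-stage rule at SD 16, and 95.3% against 98.1% at SD 14. Under left skew the two-stage rule rejects more often, but only alongside its inflated error. The change is one of wording. The sponsor must still decide whether the Protocol edit alters a principal feature (12.3) or is a significant amendment needing ethics committee submission (14.6). The SAP should be settled before it goes to HAS, which Protocol 14.7.4 places before the analyses.
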